Correlation of Audiovisual Features
With Clinical Variables and
Neurocognitive Functions in Bipolar
Disorder, Mania

01.08.2017

Study Protocol

In order to gather sociodemographic and clinical information, all patients were assessed with semi-structured interviews based on the SKIP-TURK. This form includes: identity, sociodemographic personal and family information, age at disease onset, severity, clinical presentation and used treatments.

Thirty-five male and sixteen female patients who were diagnosed as BD type I, manic episode according to DSM-5 in the mental health service of Erenkoy Mental State Hospital and 24 male and 16 female healthy controls matched for age, gender, educational status were included. During hospitalization in every follow up day (0th- 3rd- 7th- 14th- 28th day) and after discharge on the 3rd month, presence of depressive and manic features for patients was evaluated using YMRS and MADRS.

Video recording is done by a presentation guide including seven tasks such as explaining the reason to come to hospital/participate in the activity, describing happy and sad memories, counting up to thirty, explaining two emotion eliciting pictures. To increase the challenge of automatic discrimination, the Control Subjects were recorded with two additional conditions, where they are asked to portray mania and depression conditions.

To provide a benchmark system and insight about the data, we investigated two different approaches. The first is a direct approach to classify video sessions into BD and normal classes, using audio-visual features. The second is an indirect approach, where we use emotion predictions for Pearson correlation analysis and regression of YMRS drop.

Speech Analysis: Acoustic Feature Extraction

Speech utterances are first separated from the video signal and then a standard set of acoustic descriptors are extracted from the audio signal using the open-source openSMILE tool (Eyben et al, 2013). In our preliminary work, we apply functionals over the whole utterance and compare performances of two sets of functionals. The first set of functionals are those used in INTERSPEECH 2010 baseline features. The second is our proposed set of 10 functionals, which we apply on all LLDs and obtain a supra-segmental feature set of $76 \times 10 = 760$ dimensions.

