Three affect classifiers are trained, one with the original 4-classes, one for valence (showing the pleasantness of emotion) and one for arousal (reflecting the activity/vitality of the speaker). The arousal and valence labels are obtained by clustering the original 4-classes into corresponding binary labels (e.g. Happy to positive valence and high arousal, Anger to negative valence and high arousal). The predictions of these affect classifiers are then used as mid-level features to classify bipolar disorder.

Video Processing and Visual Features

The faces are detected, cropped and registered using the method proposed by Xiong and De la Torre (2013) with additional procrustes analysis for frontalization as in (Kaya et al., 2015). Along with the faces, we record both the original and the aligned landmark points for subsequent geometric feature extraction. Also, we extract appearance descriptors from registered faces, using a pre-trained Deep Convolutional Neural Network (DCNN) fine-tuned on a face based emotion corpus (Kaya et al, 2017). From DCNN, we extracted 4096 dimensional features from a convolutional layer and 7 dimensional features (outputs for 7 basic emotions) from the last layer.

Neurocognitive Evaluation

Cambridge Neurophysiological Assessment Battery (CANTAB) are administered to both groups) to assess neurocognitive functions. For patients both in the manic phase(in the first week of hospitalization) and in the remission (at 3rd month after beginning of mania treatment), tests are applied. Applied four different tests and their outcome measures are explained below :

Cambridge Gambling Test: Deliberation time, quality of decision making , risk taking, aversion delay

Emotion Recognition Test: Total rate of happiness, sadness, anger,disgust, fear, surprise

Stop Signal Test: Rate of succesful stops, reaction time, delay of stop signal, reaction time for stop signal, total of true stops

Rapid Visual Processing: Outcome measures cover latency (speed of response), probability of false alarms and sensitivity.

Study groups' sociodemographic and clinical features are defined. Bipolar manic phase patients' first YMRS ratings are correlated with first week neurocognitive functions of the same group. The comparison of bipolar mania neurocognitive functions with both bipolar remission and healthy controls are evalauted. The voice analysis results correlation with neurocognitive functions in bipolar mania is examined.

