Correlation of Audiovisual Features
With Clinical Variables and
Neurocognitive Functions in Bipolar
Disorder, Mania

01.08.2017

Statistical Analysis

Speech and Video Analysis

Classification Methods

Feature vectors extracted from audio and video are modelled using Partial Least Squares (PLS) regression and Extreme Learning Machines based classifiers(Kaya et al., 2015; 2017).

Neurocognitive Evaluation

Statistical evaluation is done by using SPSS(Statistical Package for Social Sciences) for Windows 18.0 program. Categoric variables are compared with Chi-square test, qualitative variables are compared with dependent and independent sampling t-test and Mann- Whitney U test. Correlation analysis are done with Pearson and Spearman test. Statistical significance is *= $p<0.05$, **= $p<0.01$, all of tests are two-sided.

Emotion predictions for Pearson correlation analysis and regression of YMRS drop

Regression Model

YMRS score temporal change is calculated as, $t1=0$ th day, $t2=3$ rd day, $t3=7$ th day, $t4=14$ th day, $t5= 28$ th day, $t6=90$ th day and $X1=t2/t1$, $X2=t3/t1$, $X3=t4/t1$, $X4=t5/t1$ and $X5=t6/t1$. These proportions are regressed as stepwise linearly to valence, arousal and singular affect scores of first audio recording values.

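### The regression of YMRS ratios on affect scores leaves out day-0 YMRS, so a coefficient can mix relation to YMRS change with admission severity

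*SAP*

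**What the plan says.** The SAP's Regression Model section introduces the outcome with "YMRS score temporal change is calculated as, $t1=0$ th day, $t2=3$ rd day". Read literally, this equates each t with a day, but the lead-in makes clear that t1 to t6 are the YMRS scores on those days. The five outcomes are then "X1=t2/t1$, $X2=t3/t1$, $X3=t4/t1$, $X4=t5/t1$ and $X5=t6/t1", so all share day-0 YMRS as denominator.

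The model is given in one sentence: "These proportions are regressed as stepwise linearly to valence, arousal and singular affect scores of first audio recording values". No other predictor is listed.

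The protocol describes the same analysis as its indirect approach: "we use emotion predictions for Pearson correlation analysis and regression of YMRS drop". It names no covariate. It also does not say whether the drop is to be related to the scores at a given admission severity or regardless of it.

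Day-0 YMRS is available. Ratings are taken "in every follow up day (0th- 3rd- 7th- 14th- 28th day") and at the third month, and the protocol's Neurocognitive Evaluation section already uses the admission rating as an analysis variable: "first YMRS ratings are correlated with first week neurocognitive functions of the same group".

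**The concern.** Dividing by the baseline looks as if it takes admission severity out of the outcome. It does so only when follow-up YMRS is, on average, a fixed fraction of day-0 YMRS. Otherwise the ratio still depends on day-0 YMRS, and any affect score that is related to day-0 YMRS inherits that dependence.

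A reader who sees a significant affect score then cannot tell which of two things it shows: that the voice carries information about later change beyond how ill the patient was on admission, or that it reflects how ill the patient was. Because the denominator is shared, the problem can recur in all five models. Its direction can also differ between visits, which could be mistaken for an effect of affect that changes over time.

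**Working it through.** The plan gives no sample-size, power or effect figure for this regression, so there is no stated figure to reproduce.

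**Mechanism.** Let B be day-0 YMRS, Y follow-up YMRS and X = Y/B. If the mean of Y given B is α + βB, the mean of X given B is α/B + β. The term α/B vanishes only if α = 0. With α above 0 the ratio falls as B rises; with α below 0 it rises.

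**Input from the documents.** Patients: 35 + 16 = 51 ("Thirty-five male and sixteen female patients who were diagnosed as BD type I"), before any loss to follow-up. Tests are two-sided at 0.05.

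**Assumptions (the documents give no YMRS means, SDs, correlations or reliability).**
- Day-0 YMRS: mean 30, SD 7.
- Follow-up mean (SD): 26 (8) at day 3, 20 (8) at day 7, 14 (8) at day 14, 6 (5) at days 28 and 90.
- r is the affect/day-0 correlation; rho is the day-0/follow-up correlation.
- There is one pre-specified affect score, and it has no association with follow-up YMRS given day-0 YMRS.

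**Where the ratio is about free of day-0 YMRS.** The slope rho × SD_follow-up / 7 must equal mean_follow-up / 30, so rho = (mean_follow-up × 7) / (30 × SD_follow-up):
- Day 3: 26 × 7 / (30 × 8) = 182/240 = 0.76
- Day 7: 20 × 7 / (30 × 8) = 140/240 = 0.58
- Day 14: 14 × 7 / (30 × 8) = 98/240 = 0.41
- Days 28/90: 6 × 7 / (30 × 5) = 42/150 = 0.28

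**Simulated rate of p<0.05 for the affect score, ratio model without day-0 YMRS (n = 51).**

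| rho at day 3 / 7 / 14 / 28-90 | r = 0.3 | r = 0.5 |
|---|---|---|
| 0.8 / 0.6 / 0.4 / 0.2 (falls over time) | 6 / 6 / 5 / 6% | 7 / 6 / 6 / 9% |
| 0.6 / 0.4 / 0.2 / 0.2 (falls, lower) | 8 / 8 / 8 / 6% | 13 / 13 / 14 / 9% |

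With rho held at 0.4 at every visit and r = 0.3 the rates are 13 / 8 / 5 / 5%. Over the whole grid (rho 0.2 to 0.8 at any visit) they run from 5 to 27% at r = 0.3 and from 6 to 63% at r = 0.5. Two extreme cells, both at r = 0.5, are about 46% at day 3 with rho 0.2 and 62 to 63% at days 28/90 with rho 0.8. At r = 0 the rate is 5% throughout.

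**Direction.** At r = 0.5 and rho = 0.6, significant results are nearly all negative at day 3 (12%) and all positive at days 28/90 (22%).

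**With day-0 YMRS added.** The rate is 5 to 6% in every cell, whether the outcome is the ratio or YMRS itself.

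**If day-0 YMRS is measured with error** (r = 0.5, rho = 0.6; affect and follow-up now both depend on true severity and are otherwise unrelated):

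| Reliability | Adjusted | Unadjusted, day 3 | Unadjusted, days 28/90 |
|---|---|---|---|
| 0.9 | 6-7% | 9% | 30% |
| 0.8 | 11-12% | 6% | 44% |
| 0.7 | 23-25% | 7-8% | 62% |

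Stepwise selection was not simulated, so these rates do not describe the full planned procedure.

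**The case against.** The strongest reply is that the plan makes no claim beyond proportional change. The protocol presents its analyses as a benchmark and a source of insight into the data. If the question is whether audio alone predicts proportional drop, the unadjusted association is the target, and a score that works through admission severity is a real finding, not a false positive. This stands. What remains is that the documents do not say which question is meant, so the result needs a label.

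Second, neither condition for mixing is shown. The title ("Correlation of Audiovisual Features" with clinical variables) says such correlations are sought, not that affect scores correlate with day-0 YMRS. The first audio recording is also not dated relative to the day-0 rating. This stands too, and it is why the size cannot be stated.

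Third, the largest rates need awkward pairings: a weak correlation over three days, or a strong one over 28 to 90 days. With a correlation that falls over time, most of the inflation goes. This is accepted, although the falling pattern is itself an assumption.

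Fourth, adjustment is not uniformly better. At reliability 0.7 it gives about 24% against 8% at day 3. It clearly helps at days 28/90. This supports reporting both models rather than replacing one with the other.

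**Conclusion.** The point holds as a possibility that the plan leaves open, not as a demonstrated bias. Mixing needs an affect score related to day-0 YMRS and a follow-up score not proportional to it. Under the assumed values with r of 0.3 to 0.5, the unadjusted rate is about 5 to 14% when the day-0/follow-up correlation falls over time, and about 45 to 63% only in extreme cells. With day-0 YMRS in the model it is about 5% if that rating is free of error.

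A reader might infer that the planned regression is invalid, or that about half of its significant results would be spurious. The documents support neither. They give no YMRS distribution or correlation that would place the study in an extreme cell, and they do not claim an effect independent of severity. A reader might also infer that adjustment settles the matter; with an imperfect day-0 rating it does not.

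The analysis is exploratory and no primary endpoint is named. The consequence is a misread coefficient, so priority is low to moderate.

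**What to change.** Add to the SAP's Regression Model section:

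- For each of X1 to X5, fit a second model with day-0 YMRS forced in first (SPSS block 1, Enter) and the affect scores in block 2. Day-0 YMRS must be forced, because as a stepwise candidate it could be dropped.
- Report it beside the planned model, which is labelled *not adjusted for admission severity*.
- Claim a relation to YMRS change beyond admission severity only from the adjusted model.
- State two limits. Error in day-0 YMRS leaves residual mixing and can make adjustment worse at early visits. Inflation from stepwise selection is not removed.

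The cost is SAP wording, one degree of freedom per model (with one affect score and 51 patients, 51 − 2 = 49 residual degrees of freedom become 51 − 3 = 48) and a second set of five models. No new data are needed, and X1 to X5 stay as outcomes.

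### Stepwise selection of affect scores, with no allowance for it, makes the p-values and R² of each retained YMRS-ratio model too favourable; five ratios separately raise the chance of a false lead

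*SAP*

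**What the plan says.** The SAP, under Regression Model, divides the YMRS score at days 3, 7, 14, 28 and 90 by the day-0 score, giving ratios X1 to X5. The modelling plan is then one sentence: "These proportions are regressed as stepwise linearly to valence, arousal and singular affect scores of first audio recording values".

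The candidate predictors come from the Protocol's speech work: "Three affect classifiers are trained, one with the original 4-classes, one for valence", and a third for arousal. The patient sample is in the opening section of the Protocol: "Thirty-five male and sixteen female patients who were diagnosed as BD type I", so 35 + 16 = 51 at most. X5 also needs the rating made "after discharge on the 3rd month", so fewer may contribute to it.

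For this regression neither document gives:
- entry or removal criteria;
- the number of candidate scores;
- a main ratio among the five;
- an adjustment for selection or multiplicity;
- any validation or shrinkage.

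The only significance thresholds (p<0.05 and p<0.01, where "all of tests are two-sided") stand in the SAP under Neurocognitive Evaluation.

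**The concern.** Stepwise entry picks the score that fits best and then tests it as though it had been the only candidate. The printed p-value ignores the search, and R² is computed only for models whose sample correlation was large enough to pass entry. Both therefore err in one direction.

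The five ratios raise a different problem. They multiply the opportunities for a chance finding and flatter the best-looking result, but leave the p-value and R² of any one fixed model unchanged.

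At stake is whether a reader can take a reported affect predictor of YMRS change, and its R², at face value. No treatment decision in the documents depends on it.

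**Working it through.** The plan gives no power, error rate or expected R² for this analysis, so there is no figure to reproduce.

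**Inputs from the documents.** Five outcomes with a common denominator; n at most 51; predictors are valence, arousal and singular affect scores.

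**Assumptions, because the documents are silent.**
- Candidates: 3 (valence, arousal, one affect score) to 6 (valence, arousal, four class scores).
- Entry at 0.05 or 0.01.
- Correlation between scores 0 to 0.7, and between outcomes 0.3 to 0.9.
- n=35 as an example of incomplete data.

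**Step 1. Selection alone, one ratio, no true association.** With k independent scores and entry level a, the chance that something is retained is 1 − (1 − a)^k.
- a=0.05: 1 − 0.95^3 = 14.3%; 1 − 0.95^6 = 26.5%.
- a=0.01: 1 − 0.99^3 = 3.0%; 1 − 0.99^6 = 5.9%.

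Simulation over the assumed score correlations gives about 11–27% and 2.4–6%. The low ends belong to three scores correlated 0.7, the high ends to six weakly correlated scores.

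**Step 2. Five ratios.** If the ratios were also independent, at least one model would be non-empty with probability 1 − 0.95^15 = 53.7% (three scores) or 1 − 0.95^30 = 78.5% (six). The ratios are correlated, so the simulated figures are lower: about 21–76% at entry 0.05 and about 5–25% at entry 0.01. For comparison, five independent single tests without selection give 1 − 0.95^5 = 22.6%.

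**Step 3. R².** A single score passes entry only if R² ≥ t²/(t² + n − 2), with t the two-sided critical value on n − 2 degrees of freedom.

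| n | entry | t² | minimum R² |
|---|---|---|---|
| 51 | 0.05 | 4.04 | 4.04/53.04 = 0.076 |
| 51 | 0.01 | 7.18 | 7.18/56.18 = 0.128 |
| 35 | 0.05 | 4.14 | 4.14/37.14 = 0.111 |
| 35 | 0.01 | 7.47 | 7.47/40.47 = 0.185 |

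These floors apply whatever the truth. In simulated stepwise models with true R² of 0, mean R² of the non-empty models is about 0.11–0.13 (entry 0.05) and 0.16–0.17 (entry 0.01) at n=51, and about 0.16–0.18 and 0.23–0.24 at n=35. With selection repeated inside each of 10 folds, cross-validated R² is about zero or slightly negative. How far below zero depends on whether the reference is the training-fold mean or the overall mean.

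**Step 4. Does a remedy hold its error rate?** A joint test of two forced-entry scores with Holm over five ratios rejects at least one ratio in about 2–5% of null data sets. Permuting patients' sets of scores, with the largest absolute score–ratio correlation as the statistic, gives 4.3–5.6%.

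**The case against.** The strongest reply is that this is exploratory work. The Protocol introduces the audiovisual analyses "To provide a benchmark system and insight about the data", names no primary ratio and claims no confirmatory result. Strict familywise control over five correlated visits is then partly a matter of preference. That stands, and it limits the severity. However, the SAP does not label this regression exploratory, and a label would not repair the p-value or R² of a selected model.

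The sizes also rest on assumptions. The Protocol derives valence and arousal labels by grouping the same four classes, so equally correlated scores are a simplification. The upper ends (27% and 76%) need six weakly correlated scores. This stands for the size; the direction was the same in every setting tried.

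A reader might infer three stronger things that the documents do not support:
- *The five ratios bias each model's p-value and R².* Only selection does that.
- *The SAP declares these predictors significant at p<0.05.* The thresholds belong to another section, and the regression paragraph commits to no p-value, R² or threshold. Such outputs are likely from a stepwise regression, but that is inference.
- *Any predictor found will be spurious.* The calculation assumes no true association and says nothing about whether one exists.

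**Conclusion.** The point holds for selection. Following the plan as written gives p-values and R² that are too favourable for each retained model, because predictors are chosen and assessed on the same patients, 51 at most, with no correction or validation. The added chance of a false lead over five ratios is real but is a separate matter.

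Confidence is high for the direction. The sizes are illustrations that depend on unstated candidate counts, entry rule, correlations and complete-case n, not estimates for this trial. Given the benchmark purpose, this is a modest fault that should be corrected before the regression is reported.

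**What to change.** Choose one of two routes.

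1. **Replace stepwise entry.** Fit one forced-entry model per ratio with the affect scores fixed before the regression is run. An example is valence and arousal, with the singular affect scores in a second such model or labelled exploratory. The SAP names all these scores equally, so the split is a choice for the study team. Test the scores jointly and apply Holm over the five ratios.
2. **Keep stepwise selection.** Label retained predictors exploratory. Give one global p-value by permuting patients' affect-score sets, covering all scores and ratios. Report R² cross-validated with selection repeated in every fold, and state the reference mean.

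On either route, state any entry and removal rules used and report every score tested. Neither route validates an individual predictor: the joint test does not say which score matters, and the permutation test is global.

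**Cost.** SAP wording and a little analysis time, with no new data. Reported R² will be lower and fewer results nominally significant. As an illustration at n=51, if one of two scores truly correlates 0.3, 0.4 or 0.5 with all five ratios, the two-score joint test with correction declares at least one ratio in about 36–63%, 66–91% or 90–99%. The lower figures apply at outcome correlation 0.9 and the higher at 0.3.
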